3.6. Blood Collection for Plasma and Serum Storage

Participant blood samples will be collected by venipuncture into an EDTA and Serum Separator collection tube. For efficiency, all plasma and serum specimens will be processed in the same manner. After blood draw procedures, specimens will be centrifuged within 60 minutes of collection, with plasma or serum aliquoted into 2.0mL cryovials for storage at -80°C. Specimens will be labeled with PID, study, date, and visit type, but will not include any individual identifying information. Please see the study MOP for additional step by step details on blood specimen processing, storage and shipping instructions.

3.7. Clinical Management of Adverse Events or Other Disease Events

Clinical events and side effects related to PrEP will typically be managed in the context of clinical care that participants are receiving, and will not involve study staff. However, if symptoms or events are identified during the context of study visits, research staff will refer participants for clinical care at HH clinical facilities or their primary provider. HHRI research visits occur in the same clinic that HH HIV and PrEP services are delivered, and across the street from the Hennepin County Public Health Clinic. Similarly, for any event unrelated to PrEP care research staff will also refer participants for clinical evaluation. If urgent or emergent care is required, participants will be referred to the HH urgent care or emergency department, which are located in the same facility that HHRI research visits are conducted.

In the event that HIV acquisition were to occur during the study, research staff would support immediate referral to an HIV clinic with rapid access to care and treatment (e.g., this would typically be available on the same day at the HH HIV clinic). Participants will be undergoing routine HIV testing at regular intervals as part of usual PrEP care. If participants have missed routine PrEP care visits, HIV testing will be offered in the context of any research visit upon request. The clinical context where HIV testing is performed will typically facilitate access to HIV treatment and care, but research study staff will facilitate this referral and linkage to HIV care if it has not occurred when participants are seen in research visits. Should any participant test positive for HIV in another community setting during the study, the study team will also assist with any resource information or direct referral to an HIV clinic.

3.8. Study Withdrawal

Participants may withdraw from study participation at any time. If participants elect to withdraw from the study, they will be asked if the study information and specimens collected up to that point can be used in analyses. In addition, participants will be asked if information related to their ongoing PrEP care (e.g., if they are continuing to engage in and receive care) may continue to be collected through the medical record for the duration of their previously anticipated study participation. Every attempt will be made to minimize missing data.

3.9. Study Data Storage and Retention

The original paper study data records will be archived for 7 years following completion of the study. Plasma from the optional blood draw will be stored for 20 years.

4. SAFETY AND ADVERSE EVENTS

4.1. Adverse Event Definitions

Adverse Event (AE): Any untoward medical occurrence in a clinical research participant administered an investigational product and which may or may not have a causal relationship with study participation. If a preexisting condition worsens post-enrollment (frequency and/or severity grade increases), it should be reported as an adverse event.

Serious Adverse Event (SAE): An AE that results in any of the following:

- i. Death,
- ii. A life-threatening condition,
- iii. A congenital anomaly/birth defect,
- iv. Inpatient hospitalization or prolongation of existing hospitalization,
- v. Persistent or significant disability/incapacity,
- vi. An important medical event that, based upon appropriate medical judgment, may jeopardize the patient or subject and may require intervention to prevent one of the outcomes listed above.

Grading Adverse Events: There are five severity grades that can be assigned to adverse events, which are defined as follows:

- i. Grade 1 = Mild
- ii. Grade 2 = Moderate
- iii. Grade 3 = Severe

- iv. Grade 4 = Potentially life-threatening
- v. Grade 5 = Death

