FWA:	Federalwide Assurance
GCP:	Good Clinical Practices
HH:	Hennepin Healthcare
HHRI:	Hennepin Healthcare Research Institute
HHS:	U.S. Department of Health and Human Services
HIV:	Human Immunodeficiency Virus
HSRC:	Human Subject Research Committee
IC:	Informed Consent
ICF:	Informed Consent Form
ICH:	International Conference on Harmonization
IoR:	Investigator of Record
IRB:	Institutional Review Board
ISO:	International Organization for Standardization
LoA:	Letter of Amendment
MOP:	Manual of Operating Procedures
MSM:	Men who have sex with men
NIAID:	National Institute of Allergy and Infectious Diseases
NIH:	National Institutes of Health
NIMH:	National Institute of Mental Health
OHRP:	U.S. Office for Human Research Protections
PI:	Principal Investigator
PK:	Pharmacokinetic
PrEP:	Pre-exposure prophylaxis
PrEP iTI:	the 'PrEP it together' mobile intervention
SAE:	Serious Adverse Event
SDSU:	San Diego State University
SOP:	Standard Operating Procedure
STI:	Sexually Transmitted Infection
SUSAR:	Suspected, Unexpected Serious Adverse Reaction
TDF:	Tenofovir disoproxil fumarate
TAF:	Tenofovir alafenamide
WHO:	World Health Organization
YMSM:	Young men who have sex with men

ii. PROTOCOL SUMMARY

Category	Description
Full Title	Connecting Youth and Young Adults to Optimize PrEP Adherence and Care: Testing the Efficacy of the PrEP iT! Intervention
Short Title	Prep it Together
Clinical Trial Phase	Phase 2
IND Sponsor	N/A
Conducted By	San Diego State University Hennepin Healthcare Research Institute
Lead Investigators	[name] (PhD), [name] (MD, MS)
Sample Size	85 participants (5 Usability, 80 trial)
Study Population	Younger men who have sex with men (MSM), ages 18-29 years
Accrual Period	Anticipated enrollment 1 year
Study Design	Randomized Clinical Trial
Study Duration	6 months
Intervention	PrEP mobile intervention vs. Usual Care
Primary Objective	Feasibility (via recruitment and study retention) and acceptability (via System Usability Scale) of the PrEP iT! intervention
Key Secondary Objectives	Adherence, as self-reported in the mobile intervention Adherence, objective as measured via TFV blood levels Linkage and follow-up with PreP medical care Stigma-related concerns

[figure not shown]
iii. GENERAL STUDY DESIGN SCHEMATIC:

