Young MSM on PrEP face traditional and stigma-related adherence barriers, which have slowed PrEP scale-up for YMSM and may limit the public health impact. Data from 2 PrEP trials with YMSM by Hosek and colleagues^{16, 17} inform this study. In ATN 110,¹⁷ 200 18-22 year olds were provided PrEP and followed for 48 weeks, with monthly visits through week 12, followed by quarterly visits thereafter. Protective drug levels (≥ 4 doses per week) decreased from 56% at week 4 to 34% at week 48, with a noticeable drop-off when quarterly visits were implemented. The ATN 113¹⁶ trial showed that among 76 15-17 year olds, protective adherence decreased from 60% at week 4 to only 28% by week 48. Similar to ATN 110, the drop in protective TFV levels was apparent after youth transitioned from monthly to quarterly visits. Youth in both studies reported typical adherence barriers (e.g., pill size, too busy, forgetting, change in routine). Additionally, they reported PrEP-related stigma concerns, such as worrying that others will think they are HIV+ or find out that they are having sex with men. This study protocol will evaluate the PrEP-iT mobile intervention as a youth-specific strategy to improve PrEP adherence and retention in PrEP care.

Summary of the scientific premise:

- YMSM are at the highest risk for HIV acquisition in the US, and are the focus of this study.
- PrEP is a highly effective prevention strategy, but requires adherence and retention to care.
- YMSM require frequent, developmentally-appropriate supports that address traditional and stigma-related barriers to achieve full PrEP adherence and retention in care

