2.3. Eligibility Criteria

Inclusion criteria:

- 1) Prescribed PrEP by a healthcare provider;
- 2) Self-reported 18-29 years of age;
- 3) Assigned male at birth;
- 4) Current male gender identification;
- 5) Gay, bisexual or other non-heterosexual identity or has had sex with a man in the past year;
- 6) HIV negative (HIV negative test in the past 3 months)

- 7) Either started or restarted PrEP in the past 30 days or started PrEP more than 30 days ago and self-reports not always taking PrEP in the past 30 days;
- 8) English-speaking (as the intervention will be built in English);
- 9) Able to meet with project staff at baseline and follow-up visits;
- 10) Regular access to SMS or the internet, either through a mobile device, tablet computer, and/or desktop or laptop computer.

Additional exclusion criteria:

- Not prescribed PrEP by a healthcare provider;
- HIV positive (by a reactive HIV antibody or detectable HIV RNA level);

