2.5. Study Intervention (PrEP-iT! mobile intervention)

➤ PrEP Adherence, PrEP Appointment, and Sexual Activity Self-Monitoring: Participants will be able to report their daily adherence to PrEP and their healthcare attendance through a simple interface in the app homepage. Participants will regularly receive messages that reflect their level of PrEP adherence. For example, if they have taken PrEP 5 days in a row, they would get a message stating "Great job [username], you've taken PrEP 5 days in a row!". If, for example, they missed their PrEP doses for 2 days, a message would appear stating, "Looks like you haven't taken PrEP in a few days – tell us reasons why?" The participant would then see a list of the most common reasons he may be missing doses, including:

- I forgot
- I didn't have it on me when I usually take it
- I ran out of PrEP
- Having trouble paying for it
- I'm not having sex
- I was traveling and didn't bring it
- I was drinking or using a drug and forgot to take it
- I'm in a monogamous relationship
- I don't like the way it makes me feel

The participant would then be provided a list of resources in the app that addressed that barrier.

Participants will be able to input their next PrEP healthcare appointment and have the option of placing that appointment on their calendar. They are given the option to customize how that appointment will appear on their calendar to protect their confidentiality. Finally, participants will be given the option to self-monitor their sexual activity. If they choose to, then this interface will appear below the PrEP adherence interface (if they do not activate this option, then they will not see it). The sexual activity self-monitoring will use the same simple interface as the adherence self-monitoring.

- PrEP iT! Tips: We will develop *PrEP iT!* “tips” to provide YMSM with information, motivation, and behavioral skills related to PrEP knowledge, attitudes, and stigma profile; PrEP healthcare engagement; and sexual risk. As we have done in prior studies, research staff created approximately 150 “tips,” which are pieces of content in the form of text, videos, GIFs, and links. Participants can browse these tips through a simple interface or through a key word search.

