- Text Messages for PrEP Adherence and Healthcare Appointments: Text messages will be sent as reminders to log into the site when a participant hasn’t done so in the prior week. Text messages are generic to minimize any potential disclosure. If the participant chooses, they may also receive a generic SMS reminders to attend their upcoming appointment.
- Ask the Expert: Participants will be able to send an anonymous question within the *PrEP iT!* app (that will send an email to research staff with no identifying information about the user) about PrEP, PrEP care, sexual health, or other health topics relevant to their wellbeing. Research staff will triage the question to the investigator with expertise in that area who will respond within 48 hours by posting the anonymous question and the expert answer to the community wall so that all users to may view it. This feature is similar to the “Ask the Expert” feature commonly used on health websites.
- Levelling Up: Gamification components will be used to motivate participants to engage with *PrEP iT!* Users will move to higher levels as they interact with *PrEP iT!* With each new level, users will be able to unlock new features (e.g., color themes) to motivate them to engage with *PrEP iT!* Users will be able to see what level they are currently at and how many points they need to reach the next level in the profile area.

Possible risks associated with the PrEP iT! mobile intervention, or study participation more broadly, are outlined with the study ICF (appendix A).

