A complete list of study visit procedures, data collection, and evaluations performed at Screening, Enrollment and/or Follow-up study visits is listed below in **Table 2**.

Table 2: Study Visit Procedures and Evaluations

Measure	Screening Assessment	Enrollment Visit	3 Month Visit	6 Month Visit
RCT online screener	X			
Informed Consent		X		
Verification of eligibility		X		
Randomization		X		

Participant and clinical data				
Demographic information	X			
HIV status	X	X	X	X
PrEP medications and strategy		X	X	X
Medical history		X	X	X
Clinical labs		X	X	X
Disease or clinical events		X	X	X
Surveys Items/Scales				
Demographics and Baseline Characteristics		X		
Technology Use Questions		X	X	X
eHealth Literacy		X	X	X
HIV Negative Cascade		X	X	X
U=U Questions		X	X	X
Substance Use		X	X	X
Sexual Risk Behavior		X	X	X
Mental Health		X	X	X
Social Support		X	X	X
Technology Use Questions			X	X
Intervention Acceptability			X	X
Exit Interview				X
Specimen collection				
Dried Blood Spot Collection		X	X	X
Blood for Storage		X		X

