4.2. Adverse Event Data Collection and Documentation

Data Collection: In addition to a medical history, clinical laboratory data will also be collection at enrollment. Following enrollment, information will then be collected on any new adverse event that occurs within 30 days following study visit procedures.

Documentation: Information on adverse events will be recorded on study visit CRFs (through the online REDCap interface). An assessment will be made by study investigators with respect to the severity grade and relationship of the AE to study participation (see 4.2 below).

Additional information ascertained for each adverse event includes: a) date of onset, b) relationship to study participation (see section 4.3 below), c) any action taken on study procedures, d) the outcome of the adverse event (e.g., resolved or ongoing), and e) whether the adverse event qualifies as a serious adverse event (including the SAE criteria fulfilled).

A narrative is required and is to be included in source documentation for all serious adverse events, as well as any other untoward events involving risks to participants that is unanticipated or unexpected and are reasonably believed to be related to research participation. The circumstances surrounding these events should be reported using the serious adverse event CRF, and reviewed with the principle investigator as soon as the event is known.

NOTE: *information on adverse event do NOT need to be reported if \leq grade 2.*

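### The adverse event definition is drug-trial wording that does not fit an app trial, and foreseeable disclosure and privacy harms have no definition and no named, systematic collection by arm

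*Combined protocol and SAP*

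**What the plan says.** **Definition.** Section 4.1 defines an adverse event as "Any untoward medical occurrence in a clinical research participant administered an investigational product". It adds that a causal link to study participation is not needed and that worsening of an earlier condition after enrollment counts. The seriousness criteria are medical, and the severity scale runs from mild to death.

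**What is tested.** The Protocol Summary gives the intervention as "PrEP mobile intervention vs. Usual Care". PrEP comes from outside the trial: the first inclusion criterion in section 2.3 is "Prescribed PrEP by a healthcare provider". No investigational product is defined.

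**Disclosure and privacy.** Section 2.5 states: "Text messages are generic to minimize any potential disclosure". Of calendar entries it says: "They are given the option to customize how that appointment will appear on their calendar to protect their confidentiality". Section 3.4 expects the program to be classed as collecting personally identifiable information, because it holds a phone number. Section 1.1 reports that youth in two earlier PrEP trials described "worrying that others will think they are HIV+ or find out that they are having sex with men".

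**Collection and reporting.** Table 2 (section 2.7) has a row for "Disease or clinical events" at enrollment, 3 and 6 months. Section 4.2 collects new adverse events within 30 days after study visit procedures and exempts grade 2 and below from reporting. It also requires a narrative for "any other untoward events involving risks to participants that is unanticipated or unexpected", provided the event is reasonably believed to be related to the research. Section 4.4 places unanticipated problems in an annual aggregate report to the IRB.

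**The concern.** The definition has two conditions, and neither suits this trial. The first is receipt of an investigational product. Controls receive none, although they share the surveys, the dried blood spot collection (by mailed kit when a visit is online) and the optional blood draws. The second is that the occurrence be medical. The harm that the app's design most visibly guards against is someone learning that a participant takes PrEP or has sex with men, and that is not a medical occurrence.

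At stake is what the pilot can tell the larger trial. Section 2.1 says the pilot is meant to inform a subsequent trial and bring unforeseen challenges to light. If disclosure harms surface only when someone volunteers them and staff judge them unexpected, few or no reports would say little about how often they occur, and nothing about whether the arms differ.

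**Working it through.** The plan gives no figure on this point, so there is none to reproduce. The check is mainly a comparison of sections, followed by a short illustration.

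**1. Who is covered.** Section 5.2 assigns participants to the app plus usual care or to usual care only. If the product is taken to be a drug, the trial administers none. If the app is taken to be the product, which the documents neither state nor exclude, the intervention arm is covered and controls are not. On both literal readings controls fall outside. Sections 4.2 and 4.3, by contrast, tie collection to study visits and relatedness to study participation, with no restriction by arm. Section 4 is therefore not consistent about who is covered.

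**2. What is covered.** Disclosure of PrEP use or sexuality, a resulting conflict, or a loss of confidentiality is not in itself a medical occurrence, and it meets no seriousness criterion unless it has a medical consequence.

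**3. The other route.** The narrative clause in 4.2 and the annual report in 4.4 are not limited to medical events, to product recipients or to one arm. The narrative clause has two conditions: the event must be unanticipated or unexpected, and it must be believed related to the research. A disclosure harm that the design already mitigates may be judged anticipated. The outputs are narratives and an aggregate report, not a count by arm.

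**4. Named collection.** No outcome in section 2.6, analysis in section 5.3 or row in Table 2 names disclosure or privacy harm. The nearest outcome, stigma-related barriers, concerns barriers and not harm events.

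**5. If staff treated disclosure as an adverse event anyway.**
- Events at grade 2 or below would not need to be reported.
- Within six months of follow-up, the 30-day windows after the enrollment and 3-month visits cover about 2 × 30 = 60 of about 180 days, or one third. The window after the 6-month visit falls beyond follow-up. The app is available throughout.

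**6. What asking would give (illustration only).** Inputs are 40 participants per arm (section 5.1) and 70% retention, the lower edge of the modest-feasibility band in section 5.3, which gives 0.70 × 40 = 28. If n app users answer and none reports an event, the exact one-sided 95% upper bound on the rate is 1 − 0.05^(1/n).

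| App users answering | Upper bound with zero events |
|---|---|
| 40 | 1 − 0.05^(1/40) = 7.2% |
| 28 | 1 − 0.05^(1/28) = 10.1% |

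Where participants are not asked, the number who would have answered no is unknown, so no such bound can be formed.

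**The case against.** A reader might infer that no adverse event can ever be counted in this trial, that none of the 80 participants meets the definition, or that the pilot must report zero events. The documents do not support this.

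- Sections 4.2 and 4.4 give unexpected, research-related events a route in either arm.
- Sections 4.2 and 4.3 work from study visits and study participation, and Table 2 collects clinical events without restriction by arm. Staff following them would probably record medical events in controls too.
- The app could be read as the product.

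Other points on that side also stand.

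- Mitigating a hazard does not prove that an actual breach would be classed as expected. Section 2.5 refers to the consent form for the risks, and that form is not in the text available here.
- Texts are generic, and appointment texts and calendar entries are optional, so the app's disclosure risk should not be exaggerated.
- The worry quoted from section 1.1 was reported as a concern about PrEP in earlier trials, not as a risk of this app.
- Table 2 rows are headings. Stigma is a secondary outcome with no row of its own, and the acceptability items and exit interview have unseen content. One can say only that no row names disclosure.
- Section 5.3 plans no comparison of adverse events, and the primary outcomes are unaffected.

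These points limit the finding but do not remove it. The alternative route depends on expectedness, relatedness and someone volunteering the event, and it yields no count by arm.

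**Conclusion.** The concern holds in a limited form. The wording of section 4.1 does not fit this trial: read literally it omits usual-care controls, and it omits non-medical harms. Unexpected, research-related events have a reporting route in both arms. Foreseeable disclosure and privacy harms have no definition and no named, systematic collection by arm, and if treated as adverse events they would meet the grade 2 floor and the 30-day window.

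No stated sample size, power figure or planned analysis changes. The loss is in safety information for the next trial. The 7.2% and 10.1% bounds show only what a zero count among 40 or 28 responding app users would support. They assume independent participants and truthful answers, and they do not estimate the true rate, for which the documents give no figure. The conclusion also assumes that the consent form, the manual of procedures and the survey instruments, none of which could be examined, do not already supply such questions.

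**What to change.** 1. In section 4.1, replace the product-administration condition with *randomized to either arm*, in line with the participation-based wording of 4.2 and 4.3.
2. Add a social-harm category: unwanted disclosure of PrEP use, sexuality or presumed HIV status; resulting conflict; loss of confidentiality. State that it is exempt from the grade 2 floor, the expectedness condition and the 30-day window.
3. Put two or three fixed items on these harms into the existing 3- and 6-month surveys in both arms, each covering the time since the last visit. If the surveys already contain such items, cite them in section 4.
4. Report, by arm, the number of participants with at least one such event and the number who answered. A descriptive table is enough.

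The cost is amendment wording, a slightly longer survey at visits already scheduled, one extra table and more recorded harms. No change to sample size or clinical management is needed.
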